### 1.2 Secondary Objectives

- 1.2.1 To estimate the time to neurocognitive decline with GBM receiving chemoradiotherapy and Ramipril. Decline will be defined as the time at which a change greater than the reliable change index for any of the individual cognitive tests is experienced for a particular patient.
- 1.2.2 To estimate the effect of treatment with Ramipril on and variability of specific non-memory cognitive functions including attention, executive function, visuo-motor skills, working memory, a screening measure of global cognitive function, mood, quality of life, fatigue and sleep disturbance.
- 1.2.3 To collect preliminary data on the presence of apolipoprotein epsilon (ApoE) isoform 4 serum (peripheral blood lymphocyte) test positivity as measured by quantitative PCR.
- 1.2.4 To estimate neurocognitive function in surviving patients at the 4 month post RT endpoint.
- 1.2.5 To estimate response as reported by treating physician assessments.

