Cognitive reserve (CR) refers to acquired compensatory strategies that enhance a person's cognitive and behavioral capacities. Individuals with higher CR should have less impairment because of their greater adaptive capacity. Common proxies for CR are literacy and educational and occupational attainment. Higher levels of CR have been associated with lower incident rates of age-associated cognitive impairment and longer delayed onset of dementia. CR will be examined as a susceptibility factor for RICD (we hypothesize that low CR individuals will have greater cognitive impairment at baseline than higher CR individuals).

In summary, RICD is a common problem following brain RT for GBM. It can affect various cognitive functions, and generally does not have a plateau in terms of severity after onset. Preclinical models suggest that by modifying the RAS within the brain, one can mitigate the inflammatory cascade that ultimately leads to RICD. Ramipril is a widely used safe and tolerable ACE-I that penetrates the blood brain barrier. The Wake Forest NCORP Research Base has a long history of evaluating pharmaceutical interventions that may mitigate symptoms of RICD, demonstrating our ability to conduct this current study. This proposal represents collaboration between Wake Forest investigators and the neurocognitive experts involved in the RTOG 0825 study. RTOG 0825 was a prospective, randomized phase III trial in newly diagnosed patients with glioblastoma comparing standard radiation and temozolomide therapy with

and without bevacizumab. RTOG 0825 also prospectively collected extensive neurocognitive data on all enrolled patients. The eligibility criteria and planned combined modality treatment proposed in this trial are identical to that used for the cohort of patients treated on the control arm of RTOG 0825.

Furthermore, the neurocognitive battery and times of administration proposed in this study have been harmonized with the battery and schedule utilized in RTOG 0825 thus providing an ideal modern era historical control group to appropriately compare with this pilot study population and ensure an ability to interpret the results of our proposed trial in the context of the most current understanding and effect magnitude of RICD in the GBM population.

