- (2) Negative serum or urine pregnancy test required within 14 days prior to enrollment for women of childbearing potential. Results may be used from routine local lab.
- (3) MRI/CT Brain scans at the indicated time points are considered standard of care per national guidelines. As per section 4.1.7, all available brain MRI or CT imaging reports from surgery to study completion must be submitted. This includes any post-operative or pre-radiation scan reports. Treating physician assessment of tumor response – i.e. response, progression or stable disease – will be captured for each completed imaging study.

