MRI/CT Brain: MRI Brain will be completed per standard of care at each study site. Sites are asked to provide MRI final reports with the specific visit form. As per section 4.1.7, patients who are unable to undergo MRI scanning should have CT brain scans done as per this schedule. Treating physician assessment of tumor response – i.e. response, progression or stable disease – will be captured for each completed imaging study.

Toxicity Assessments: Assessments by the study team will be done from Week 1 of RT and the start of Ramipril to 5-month post RT (end of study). This time period includes 30 days after treatment with Ramipril. Refer to section 6.2 for reported adverse events and risks when taking Ramipril.

Adverse Event Reporting: Refer to Section 10 of the protocol for specifics.

**Medication Diary:** Each patient is asked to fill in a Ramipril Medication diary and return it to the study team weekly during radiation therapy (weeks 1-6), and monthly on 1- and 4- month post RT visit. Since 2- and 3- month visits can be phone calls, the patient will need to mail back these diaries to the study team. Refer to Appendix D for a Ramipril Medication diary.

**Pill Count:** Patients will be asked to bring pill bottles to visit. Study team will count and record pills given, remaining and taken on the visit CRF.

**Ramipril Administration:** This study drug will be provided at no charge to patients for oral administration daily from Week 1 RT to post 4-month RT (Week 22). Study team will be required to order, distribute and inventory study drug. Refer to Sections 6.3 – 6.8 and for titration schedule 5.1.2 for details.

**Chemoradiation Summary:** At the RT Completion (Week 6) visit, a summary of the standard of care chemotherapy and radiation therapy will be gathered.

**Off Agent:** Use this form when a patient goes Off Agent either at the completion of study drug administration per protocol or at the time of early discontinuation. All study assessment should be continue to be completed, unless the patient is unwilling or withdraws consent. LabCorp samples do not need to be collected after the patient is Off Agent. Please use local labs to complete assessment information in REDCap.

**Off Study:** Use this form when a patient goes Off Study by either withdrawing consent or completing the study. This form serves as a way to track the patient status.

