### 8.2 Secondary Endpoints

**Participant reported outcomes (PRO):** Participant-reported outcomes will complement the neurocognitive battery. The EORTC Quality of Life Questionnaire-Core 30/Brain Cancer Module-20 (EORTCQLQ30/BN20) will measure several domains of functioning (physical, emotional, cognitive, social, fatigue, pain, etc.) (8 minutes). Each cognitive test and PRO proposed has adequate psychometric properties and has been used previously in clinical trials of oncology patients.

**Imaging:** Adequate imaging for diagnostic, treatment planning and follow-up imaging will follow standard of care practices and will include contrast-enhanced T1-weighted MRI and T2 or FLAIR imaging. Contrast-enhanced CT will be allowed only in cases where patients are unable to undergo MRI because of non-compatible devices. MRI of the brain will be performed 1- and 4-month post-RT or until time of tumor progression, should that occur prior to the 4-month post-RT time point. Response assessment will be based on treating investigator assessment and institutional standard of care. Imaging parameters will only be utilized to measure response and progression.

**Other variables to be measured:** Sociodemographic variables to be assessed in a questionnaire at baseline will include age, education, race/ethnicity, menopausal status, co-morbid medical conditions, concomitant medication, marital status, socioeconomic status, tumor size and location. Variables to be assessed after completion of each treatment phase by treating physician include dates, dose and compliance of temozolomide administration, radiation dose, radiation dose per fraction, and radiation volume (e.g. planned treatment volume (PTV)). *Cognitive reserve* (CR) will be measured with the Shipley Scale-Vocabulary with educational (years in school) and occupational attainment (standardized 8-level classification) also measured as proxies for CR.

**Biomarkers:** APOE genotype, a risk factor for cognitive impairment and dementia, will be derived from

whole blood samples taken at baseline at the site of study enrollment. See Section 10.1 for sampling handling and processing.

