Treating physician response rate will be summarized at each timepoint with corresponding 95% confidence intervals. Time to neurocognitive failure will largely follow the method reported in Gilbert *et al.* for evaluating if there is meaningful difference in the risk of cognitive progression. Neurocognitive failure will be defined as the first decline on reliable change index on any of the individual cognitive tests. In the presence of competing risks for neurocognitive failure, including GBM-related mortality risk, we plan to explore the use of competing risks methods for both descriptive statistics (e.g. the Kaplan-Meier curves) and competing risk regression analysis. Competing risk methods are needed because time to neurocognitive failure is not independent of mortality and ignoring events from competing risk will lead to biased results. The competing risk analysis will be based on the method proposed in Gray and Fine and Gray using SAS macro %CIF and PROC PHREG. Patient reported outcomes will be assessed as described above for the CTB COMP.

Exploratory subgroup analyses will be conducted for all 4 month post RT outcomes by whether the patient received Optune® (also known as Tumor-Treating Fields or TTFIELDS) as part of their standard treatment following RT. Differences by Optune® for continuous outcomes will be assessed by two-sample t-tests where parametric assumptions hold; otherwise Mann-Whitney U tests will be applied. For categorical outcomes, Fisher's exact or Chi-square tests will be implemented. Corresponding 95% confidence intervals will also be presented for outcomes within each subgroup.

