## **12.7 Evaluation of Toxicity**

### **Evaluation of Toxicity and Adverse Effects of Ramipril**

All patients will be evaluable for toxicity from the time of their first treatment with Ramipril. Toxicities will be quantified using the CTCAE v5.0 for Toxicity and Adverse Event Reporting. Fisher exact tests will be used to assess treatment differences in the incidence of individual toxicities, and logistic regression will be used to assess treatment differences in the incidence of any grade 3 or higher toxicity possibly, probably or likely related to Ramipril adjusting for baseline patient characteristics. In order to rule out cytoprotection of tumor by Ramipril, response rates will be compared to historical controls from RTOG 0825.

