## **12.8 Evaluation of Response**

Tumor response assessment will be based on treating investigator assessment and institutional standard of care and this assessment will be captured in this study.

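### Section 12.7 claims more than it can deliver: comparing locally scored response with RTOG 0825 cannot rule out tumour protection by Ramipril

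*Combined protocol and SAP*

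**What the plan says.** The plan uses tumour response in two ways.

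The first is estimation. Secondary objective 1.2.5 reads "To estimate response as reported by treating physician assessments", and 12.4 follows it: "Treating physician response rate will be summarized at each timepoint with corresponding 95% confidence intervals".

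The second is a safety conclusion. Section 12.7 states: "In order to rule out cytoprotection of tumor by Ramipril, response rates will be compared to historical controls from RTOG 0825".

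Both uses draw on the same data. Note (3) to the Schedule of Events (7.1) says: "Treating physician assessment of tumor response – i.e. response, progression or stable disease – will be captured for each completed imaging study". Section 8.2 gives the standard: "Response assessment will be based on treating investigator assessment and institutional standard of care". Section 12.8 repeats this. No set of response criteria is named and no central or blinded read is planned. Section 7.3 describes what sites send in: "Sites are asked to provide MRI final reports with the specific visit form". Collection of the images themselves is not described.

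On comparability with RTOG 0825, the closing paragraphs of section 2.2 state that eligibility and combined-modality treatment are identical to the control arm, and that "the neurocognitive battery and times of administration proposed in this study have been harmonized with the battery and schedule utilized in RTOG 0825". Response scoring is not mentioned there or elsewhere as something that was aligned.

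**The concern.** A comparison with an external control is only as good as the match in how the outcome was measured. The plan takes care over this for other measures. The cognitive battery follows RTOG 0825, examiners are centrally trained and certified (7.6.1), and sites that rely on local laboratory values must also send LabCorp samples so that results can be compared across sites (section 3 and 5.2). Response has no such safeguard, although 12.7 compares it across trials.

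If the two cohorts had different thresholds for calling a response, that difference would pass straight into the estimated effect on the tumour. It could hide a real loss of response or create an apparent one. Extra patients would not remove it. The covariates pre-specified in 12.4 (MGMT methylation, KPS and extent of resection) describe the patient and the tumour, so adjusting for them would not correct it either. No sensitivity analysis for scoring is planned.

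At stake is a statement that a drug chosen for its cytoprotective action does not protect the tumour. If that statement is made without support, it could be carried into the randomized trial that this pilot is meant to inform.

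**Working it through.** **The plan's own figure.** The only sized comparison is the retention test in 12.2: 65% against 80%, one-sided 0.05, 90% power.

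- n = ((1.645 × √(0.65 × 0.35) + 1.282 × √(0.80 × 0.20)) / 0.15)² = 74.8, rounded up to 75.
- Exact check: requiring at least 56 of 75 retained gives a type I error of 0.0485 and power of 0.900.

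So 75 reproduces, but it concerns retention. The response comparison has no stated size, power or margin.

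**Inputs for response.** From the plan: 75 patients. Not in the documents, and therefore assumed: the RTOG 0825 response rate (30%, with 10% to 50% as a range), the number of controls (100 to 300, with 75 as a further case), and any scoring shift (0 to 15 points).

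**Step 1: precision with identical scoring.** The 95% half-width for a difference in proportions, with p the common response rate and m the number of controls, is 1.96 × √(p(1 − p)(1/75 + 1/m)). At p = 0.30:

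- m = 100: 1.96 × √(0.21 × 0.02333) = 0.137
- m = 200: 1.96 × √(0.21 × 0.01833) = 0.122
- m = 300: 1.96 × √(0.21 × 0.01667) = 0.116

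The result depends on the assumed rate:

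| Assumed rate | Half-width, 300 controls | Half-width, 75 controls |
|---|---|---|
| 10% | 7.6 points | 9.6 points |
| 20% | 10.1 points | 12.8 points |
| 30% | 11.6 points | 14.7 points |
| 50% | 12.7 points | 16.0 points |

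At rates of 20% or more, equal observed rates leave a 10-point loss inside the interval. At 10% the half-width is below 10 points, but there a 10-point loss would mean no responses at all. All these figures assume that every one of the 75 patients can be scored. Criterion 4.1.1 admits patients after gross total resection, so the number may be smaller and the intervals wider.

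**Step 2: effect of a scoring shift, if there is one.** These figures use 75 against an assumed 300 controls and a two-sided 0.05 test. Suppose Ramipril has no effect on the tumour but this trial's sites call fewer responses than RTOG 0825 did. The chance of a false signal of harm is:

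| Stricter scoring by | Control rate 20% | 30% | 40% |
|---|---|---|---|
| 5 points | 15% | 13% | 12% |
| 10 points | 53% | 40% | 35% |
| 15 points | 95% | 78% | 69% |

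The 10-point row also gives the power to detect a true 10-point loss when scoring is identical: only 35% to 53%.

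In the other direction, suppose a true fall from 30% to 20% is met by scoring that is 10 points more lenient. The expected comparison is then 30% against 30%, and the chance of a signal of harm drops to about 2.5%.

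**The case against.** **The bias is not shown.** The documents do not say who scored response in RTOG 0825, by what criteria, or with what result. It may also have used investigator calls. A reader might infer that scoring differs between the cohorts and that tumour harm would be masked. The documents do not support that: a shift of zero is compatible with everything in them, and the direction of any shift is unknown. This objection stands. What remains is that comparability is undocumented.

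**Local scoring is a legitimate choice.** It matches objective 1.2.5 and the summary in 12.4, and the plan never promises to harmonise response. That also stands. Note (3) is not an error and there is no contradiction with section 2.2; the overstatement is in 12.7.

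**Common criteria would not rescue the claim.** A reader might infer that adopting RTOG 0825's criteria is the cure. The criteria are not in the documents. The data-sharing statement in 2.3 sits beside a description of the neurocognitive dataset and does not clearly cover response. Physicians in a single-arm trial would still know that every patient takes Ramipril. Step 1 also shows that precision alone prevents a 10-point loss from being excluded at the assumed 30% rate when the observed rates are equal. This stands too, and it is why the main remedy is to the wording.

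**The consequence is limited.** Progress to a randomized study turns on retention (1.1.1, 12.2), and 12.2 and 12.4 disclaim any declaration of efficacy. The first part is fair. The disclaimer, however, concerns efficacy and does not qualify the safety wording in 12.7.

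**Conclusion.** The point holds as a limit on what 12.7 may conclude. Response is called locally with no common criteria, the documents do not establish that RTOG 0825 was scored in the same way, and no planned analysis would separate a scoring difference from an effect on the tumour. The claim to rule out tumour protection is therefore unsupported, whatever the scoring in RTOG 0825 turns out to have been.

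The precision argument does not depend on any scoring shift. It rests on an assumed 30% response rate, 75 scorable patients and an assumed 100 to 300 controls, which give a 95% half-width of about 12 to 14 points. The scoring argument is conditional. A shift of 10 points would matter a great deal and a shift of zero not at all, and the documents do not say which applies. It would be wrong to report this as demonstrated bias or as evidence that harm has been hidden.

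**What to change.** In 12.7, replace the wording that claims to rule out tumour protection with a descriptive comparison: the difference in response rate between this trial and the RTOG 0825 controls, with a 95% confidence interval. Add a sentence saying that response was scored by treating physicians to local practice, that this may not match the scoring in RTOG 0825, and that the comparison is not intended to exclude a protective effect on the tumour. Note (3) in 7.1, 8.2 and 12.8 can stay as they are.

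Optionally, find out whether RTOG 0825's response criteria and response data can be obtained, and whether the criteria can be applied to routine scans. If so, have the treating physician also record the Week 10 and Week 22 calls by those criteria, next to the local call. This would remove one source of non-comparability. It would not improve precision or remove knowledge of treatment, so the descriptive wording should stay.

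The main change costs one edit and a weaker stated safety claim. The optional addition needs extra form fields and instruction for sites; how much cannot be judged until the criteria are seen.

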## Notes:

- If RT is delayed, Ramipril will still be given and continue to be given until 4-months Post RT (Week 22). That is, the visits will be pushed out the length of the delay.
- If a patient decides to discontinue participation in study at any time prior to study completion, the entire battery of neurocognitive (except Shipley) and participant related outcomes tests and forms should be administered. (Refer to Section 8.3 for Off-Study Details)

## 7.2 Study Visit Windows

Study Visit	Visit Window
Enrollment	n/a
Baseline	≤ 14 days after Enrollment
Titration of Drug (Week 1-3)	+/- 3 days
During RT (Week 4-5)	+/- 3 days
RT Completion (Week 6)	+/- 3 days
1-month Post RT (Week 10)	+/- 7 days
2- & 3- month post RT (Week 14 & 18) Phone calls	+/- 7 days
4- month post RT (Week 22)	+/- 7 days
5- month post RT (Week 26) Phone Call	+/- 7 days

## 7.3 Evaluations and Procedures

Eligibility/Enrollment: Patient must sign the IRB approved study informed consent before any study-related evaluations or procedures are complete. Then, study team should complete the Enrollment Checklist to determine if a patient is eligible for the study before they are enrolled. Patients should be enrolled electronically as described in Section 13.3.

Patient Demographics: Patients should complete the Patient Demographic and Health Related Behaviors Form at Enrollment.

Medical History: Medical History should be performed within 14 days prior to enrollment. This Medical History should be reviewed and updated at the following 2 visits: Months 1- and 4- post RT. Forms for each visit have required data collected.

Concurrent Medication & Supplements: Current medications should be compiled at Baseline and then updated at each study visit throughout RT. Patients should be seen by the study team at the 1- and 4-month post RT visit to update changes in medication. Patients should be called at 2- and 3- month post RT visits to determine any updates.

Physical Exam: Exams should be performed by MD, NP or PA within 14 days prior to enrollment. They should also be performed at the following 2 visits: Months 1- and 4- post RT. Forms for each visit have required data to be collected.

Blood Pressure: Blood pressure should be recorded and reviewed for any Dose Modifications (see Section 5.6) at Baseline, each week during RT (Wk 1-6) and at the following 2 visits: Months 1- and 4- post RT. Refer to Section 5.5 for criteria for Dose Modifications.

Comprehensive Metabolic Panel (CMP): Inclusive of creatinine, potassium, GFR, Total Bilirubin, AST and ALT. Labs are required within 14 days of enrollment. These labs should also be collected at Baseline, Weeks 1-6 during RT and at 1 Month Post RT (Wk 10). Refer to Section 5.5 for criteria for Dose Modifications related to labs. The CMPs for Week 1, 2, 3, 4, 5 & 6 during RT should be analyzed through LabCorp and paid by the study directly to LabCorp. If local sites perform CMPs at Week 1, 2, 3, 4, 5 or 6 during RT as standard of care, these values can be used to determine toxicity, but LabCorp CMPs should also be drawn for consistence across study sites. Sites should choose if LabCorp or local institutional lab values will be used to assess drug related toxicity that determines if dose escalation per protocol is appropriate during weeks 1-6 of RT. The same lab should perform the CMPs for Week 1-6 visits. At Baseline and 1 month post RT, standard of care local labs should be used for the study and to determine toxicity, if applicable.

In the event of inability to obtain LabCorp results in an appropriate time interval, local standard of care labs can be used for Ramipril titration decision making and other protocol related activities.

If lab abnormalities are detected that would affect the conduct of the study, treating physicians should consider whether correctable disease or treatment related toxicities (e.g. dehydration, nausea and vomiting, etc.) could be responsible. If so, clinicians should attempt to address those issues and repeat the labs within 24-48 hours for protocol decision making.

ECOG (Eastern Cooperative Oncology Group) Performance Status: Study Team should determine the patient's ECOG performance status using the chart in Appendix A at the Baseline visit.

Serum or Urine  $\beta$ HCG: A negative serum or urine pregnancy test is required within 14 days prior to enrollment for women of childbearing potential. Results will be used from standard of care local labs.

APOE Genotyping: At Baseline, a blood vial of approximately 8 ml will be taken from a vein in the arm/central line for lab analysis. Blood samples will be stored with a unique identifier and will not include any information protected by HIPAA regulations. Blood samples will be stored at Wake Forest. See Section 9.0 for specimen management.

MRI/CT Brain: MRI Brain will be completed per standard of care at each study site. Sites are asked to provide MRI final reports with the specific visit form. As per section 4.1.7, patients who are unable to undergo MRI scanning should have CT brain scans done as per this schedule. Treating physician assessment of tumor response – i.e. response, progression or stable disease – will be captured for each completed imaging study.

Toxicity Assessments: Assessments by the study team will be done from Week 1 of RT and the start of Ramipril to 5-month post RT (end of study). This time period includes 30 days after treatment with Ramipril. Refer to section 6.2 for reported adverse events and risks when taking Ramipril.

Adverse Event Reporting: Refer to Section 10 of the protocol for specifics.

**Medication Diary:** Each patient is asked to fill in a Ramipril Medication diary and return it to the study team weekly during radiation therapy (weeks 1-6), and monthly on 1- and 4- month post RT visit. Since 2- and 3- month visits can be phone calls, the patient will need to mail back these diaries to the study team. Refer to Appendix D for a Ramipril Medication diary.

**Pill Count:** Patients will be asked to bring pill bottles to visit. Study team will count and record pills given, remaining and taken on the visit CRF.

**Ramipril Administration:** This study drug will be provided at no charge to patients for oral administration daily from Week 1 RT to post 4-month RT (Week 22). Study team will be required to order, distribute and inventory study drug. Refer to Sections 6.3 – 6.8 and for titration schedule 5.1.2 for details.

**Chemoradiation Summary:** At the RT Completion (Week 6) visit, a summary of the standard of care chemotherapy and radiation therapy will be gathered.

**Off Agent:** Use this form when a patient goes Off Agent either at the completion of study drug administration per protocol or at the time of early discontinuation. All study assessment should be continue to be completed, unless the patient is unwilling or withdraws consent. LabCorp samples do not need to be collected after the patient is Off Agent. Please use local labs to complete assessment information in REDCap.

**Off Study:** Use this form when a patient goes Off Study by either withdrawing consent or completing the study. This form serves as a way to track the patient status.

